4. Place cryovials into biohazard bag and immediately freeze at -70 to -90°C.
5. Store frozen plasma until ready for testing.

IX. **Assessment of Safety, Dose Modifications and Dose Delays**

- A. This study will be reviewed by the Medical College of Wisconsin Cancer Center Data Safety Monitoring Committee (MCW CC DSMC). A summary of the MCW CC DSMC activities are as follows:
 - i. Review the clinical trial for data integrity and safety.

- ii. Review all unexpected grade 3, and all grade 4, and 5 adverse events, as well as any others requiring expedited reporting as defined in this protocol. (Grades 4 & 5 events must be reported to the DSMC within 5 calendar days of study staff's knowledge.) Review all DSM reports.
- iii. Sequential boundaries will be used to monitor the post-operative wound-complication rate. The accrual will be halted if excessive numbers of grade 3 or 4 (page 32) complications are seen, that is, if the number of complications is equal to or exceeds X out of N patients (X/N) with full follow-up (see below). This is a Pocock-type stopping boundary (Ivanova, et al. 2013) that yields the probability of crossing the boundary at most 5% when the complications rate is equal to 50% (O'Sullivan, et al. 2002).
- iv. Accrual will halt for protocol review if 6/6 (6 patients out of the first 6), then 7/7, 8/8, 9/10, 10/11, 11/13, 12/14, 13/16, 14/18, 15/19, 16/21, 17/22, 18/24, 19/26, 20/27, 21/29, 22/31, 23/32, 24/34, and 25/35 grade 3-4 treatment related AE's.
- v. Submit a summary of any recommendations related to study conduct.
- vi. Terminate the study if deemed unsafe for patients.
- B. A copy of the MCW Cancer Center Data and Safety Monitoring Plan and membership roster will be maintained in the study research file and updated as membership changes.
- C. The committee will review reports from the study PI twice annually (or more frequently if needed) and provide recommendations on trial continuation, suspension or termination as necessary.

X. **Subject Withdrawal Criteria**

- A. This Protocol is designed for 35 patients. Accrual will terminate early based on toxicity analysis. Patients may also withdraw at any point if they wish to not be on study.
- B. Criteria for early Closure

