 - i. Greater than 2 patients who have any grade 4 or higher toxicity during radiation. If a patient has a grade 4 or higher toxicity, then they will be taken off the study, administered a lower dose per fraction per the treating physician, and the study will be closed. We do expect grade 3 skin toxicity (moist desquamation in areas other than skin folds), as many patients have tumors that extend to the surface of the skin and thus will need to be bloused to get the appropriate dose to these areas. Thus, moist desquamation often occurs.
 - ii. ≥60% of patients with post-operative wound complications.
 - iii. As mentioned above, patients may also withdraw at any point if they wish to not be on study.
- C. The research coordinator and PI will be notified of the withdrawal of a patient and the appropriate documentation will be made.
 - i. The IRB will be notified at the time of withdrawal.
- D. Subjects will not be replaced.
- E. Follow up and data collection for withdrawn subjects will terminate at the time of withdrawal.
- F. Dose Modification
 - i. If any grade 4 toxicity occurs, the dose will be modified based on the BED calculator above and the study will be closed.

XI. **Endpoint Assessment**

- A. Study Design:
 - i. This is a non-randomized Phase II pilot protocol to determine the feasibility, toxicity, and disease control (local control, overall and progression-free survival) using hypofractionated pre-operative radiation therapy in patients with primary localized STS.
- B. Primary Endpoint:

- i. The primary aim of this study is to assess local control. We expect local recurrence rates of <7%. Local and regional recurrence will be defined for each lesion per the treating physician(s). Local recurrence will be defined if the patient has evidence of disease on imaging (MRI or CT or PET CT) or physical exam.

C. Secondary Endpoint:

- i. The secondary objective of this study is to assess quality of life, toxicity (see iii), disease-free survival and overall survival. Disease-free survival is defined as the time from enrollment until documented disease-recurrence or death, whichever occurs first. Patients who are disease-free and alive at the time of analysis will be censored at the time of their last follow-up. Patients will be followed for disease-free survival for a minimum of 2 years.
- ii. Quality of life will be assessed via the FACT-L forms and given at the specified time points above.

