APPENDIX III

CTCAE 4.0 Toxicity Grading

Edema

Grade	Toxicity
1	5 - 10% inter-limb discrepancy in volume or circumference at point of greatest visible difference; swelling or obscuration of anatomic architecture on close inspection
2	>10 - 30% inter-limb discrepancy in volume or circumference at point of greatest visible difference; readily apparent obscuration of anatomic architecture; obliteration of skin folds; readily apparent deviation from normal anatomic contour; limiting instrumental ADL
3	>30% inter-limb discrepancy in volume; gross deviation from normal anatomic contour; limiting self care ADL
4	-
5	-

Definition: A disorder characterized by swelling due to excessive fluid accumulation in the upper or lower extremities.

Radiation Dermatitis

Grade	Toxicity
1	Faint erythema or dry desquamation
2	Moderate to brisk erythema; patchy moist desquamation, mostly confined to skin folds and creases; moderate edema
3	Moist desquamation in areas other than skin folds and creases; bleeding induced by minor trauma or abrasion
4	Life-threatening consequences; skin necrosis or ulceration of full thickness dermis; spontaneous bleeding from involved site; skin graft indicated
5	Death

Fibrosis

Grade	Toxicity
1	Mild induration, able to move skin parallel to plane (sliding) and perpendicular to skin (pinching up)
2	Moderate induration, able to slide skin, unable to pinch skin; limiting instrumental ADL
3	Severe induration; unable to slide or pinch skin; limiting joint or orifice movement (e.g. mouth, anus); limiting self care ADL
4	Generalized; associated with signs or symptoms of impaired breathing or feeding
5	Death

Post-operative Wound Complications

Grade	Toxicity
1	Incisional separation of <=25% of wound, no deeper than superficial fascia
2	Incisional separation >25% of wound; local care indicated
3	Hernia without evidence of strangulation; fascial disruption/dehiscence; primary wound closure or revision by operative intervention indicated
4	Hernia with evidence of strangulation; major reconstruction flap, grafting, resection, or amputation indicated
5	Death

Musculoskeletal Tumor Rating Scale-Upper Extremity

PAIN		FUNCTION	EMOTIONAL	HAND POSITIONING	MANUAL DEXTERITY	LIFTING ABILITY
5	No pain	No restriction	Enthused	Unlimited	Unlimited	Normal load
4	Intermediate	Intermediate	Intermediate	Intermediate	Intermediate	Intermediate
3	Modest/Non-disabling	Recreational restriction	Satisfied	Not above shoulder or no/Prosupination	Loss of fine movements	Limited

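### On the same event, denominator and look, the 60% wound-complication closure criterion (X.B.ii) is met before any halt-for-review point in IX.A.iv, and IX.A.iv mislabels the event counted

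*Combined protocol and SAP*

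**What the plan says.** Three provisions of the combined protocol and SAP deal with stopping for wound complications.

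- **IX.A.iii** states the aim: "Sequential boundaries will be used to monitor the post-operative wound-complication rate". The event is a grade 3 or 4 complication, the denominator is patients with full follow-up, and the reader is sent to the list that follows. The boundary is said to be one that "yields the probability of crossing the boundary at most 5% when the complications rate is equal to 50" per cent.
- **IX.A.iv** gives the list and its action: "Accrual will halt for protocol review if 6/6 (6 patients out of the first 6", and so on through 20 points to "24/34, and 25/35 grade 3-4 treatment related AE's". The action is a halt of accrual for review.
- **X.B.ii**, under the criteria for early closure, reads in full: "≥60% of patients with post-operative wound complications". It gives no grade, no minimum number of patients, no follow-up requirement and no looks.

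The only review frequency stated is in IX.C: "The committee will review reports from the study PI twice annually (or more frequently if needed".

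Two other places bear on the event. X.B.i says "We do expect grade 3 skin toxicity" and describes it as moist desquamation. Appendix III defines grade 3 radiation dermatitis to include "Moist desquamation in areas other than skin folds and creases". Section VI.H.ii expects wound complications in about 30-40% of patients.

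**The concern.** A stopping plan with two tiers would normally have review at the lower threshold and closure at the higher one. Here, for a like-for-like count, the order is reversed: the harsher action has the lower threshold. A committee looking at 13 wound complications in 20 evaluated patients would find the closure criterion met and the review boundary not reached, with no text to say which prevails.

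The quoted error rate is affected too. A reader will take 5% as the chance that the trial stops for wound complications if the true rate is 50%. That figure belongs to the list in isolation.

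Finally, the list is calibrated for one event and labelled with another. Grade 3 moist desquamation is a treatment-related adverse event but not a post-operative wound complication. If it were counted as IX.A.iv is worded, the boundary would be applied to an event for which IX.A.iii did not set it.

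**Working it through.** **Inputs.** The 20 X/N points (IX.A.iv); the 60% threshold (X.B.ii); the 50% reference rate and 5% crossing probability (IX.A.iii); 35 patients (X.A). X.B.ii looks are not in the documents and are assumed below.

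**Step 1: reproduce the plan's figure.** Let p be the true complication rate and f(n,k) the probability of k events after n patients without having stopped. Start from f(0,0) = 1 and use

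f(n,k) = (1 − p)·f(n−1,k) + p·f(n−1,k−1).

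At each listed N, move the probability with k ≥ X into the stopped total. At p = 0.50 the total over 35 patients is 0.0499. This agrees with the stated limit of 5%, so the list is correctly calculated.

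**Step 2: compare thresholds.** The lowest list fractions are 24/34 = 0.706, 22/31 = 0.710 and 25/35 = 0.714; the highest is 6/6 = 1.00. All 20 exceed 0.60. On the same event and patients, any count that reaches the list therefore already satisfies X.B.ii, and the converse fails.

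Events needed under X.B.ii are the smallest whole number not below 0.6n. The list has no point at n = 20 or 30. A count of 16 at n = 20 must cross at 16/21, and 22 at n = 30 must cross at 22/31, so those are the effective list values.

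| Patients evaluated | X.B.ii closure | IX.A.iv review | Closure met, review not reached |
|---|---|---|---|
| 10 | 6 | 9 | 6-8 |
| 20 | 12 | 16 | 12-15 |
| 30 | 18 | 22 | 18-21 |

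**Step 3: chance of stopping under both rules (illustration).** Same recursion, with the list checked after every patient and X.B.ii (k ≥ 0.6n) added at assumed looks of 20 and 30 patients, both rules counting the same event. The separate grade 4 and grade 5 rules are left out.

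| True rate | List alone | List plus X.B.ii at 20 and 30 |
|---|---|---|
| 35% | 0.3% | 2.2% |
| 40% | 0.7% | 6.4% |
| 50% | 4.99% | 29.4% |
| 60% | 24.6% | 68.2% |

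Other assumed looks for X.B.ii, at a true 50%, give 16.8% (only at patient 35, when accrual is over), 33.0% (after every patient from 20) and 45.4% (at 10, 20 and 30).

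**Step 4: compare the events.** IX.A.iii counts grade 3-4 post-operative wound complications and points to the list. The list in IX.A.iv ends by counting grade 3-4 treatment-related adverse events. Appendix III places moist desquamation outside skin folds at grade 3 under radiation dermatitis, in a separate table from post-operative wound complications. X.B.i expects it. It therefore counts under IX.A.iv as worded and not under IX.A.iii. The documents give no desquamation rate, so the effect on crossing cannot be sized from them.

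**The case against.** **The ordering is conditional.** IX.A.iii uses patients with full follow-up; X.B.ii says only patients. If X.B.ii were read over everyone enrolled, 9 events among 10 fully followed patients with 16 enrolled would reach the list (9/10) but not the closure criterion (9/16 = 56%). Under the broader IX.A.iv event, review could also come first. This stands. A reader might infer that closure always precedes review, but the documents support that only for a common event, denominator and look. That these must be assumed shows how little X.B.ii specifies.

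**IX.A.iii and IX.A.iv are one rule.** The cross-reference and the reproduced 5% show that the list was built for wound complications, and VI.H.vii distinguishes post-operative wound complications from acute reactions during radiation. The label in IX.A.iv is most naturally a slip. A reader might infer that two separate boundaries were intended; the text does not support that. The label still needs correcting because staff will count what it says.

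**The missing grade is partly supplied elsewhere.** VI.H.iv collects only grade 3-5 events, so in practice X.B.ii would count grade 3 or higher. That is fair, but it leaves the denominator, minimum number and looks open.

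**The conflict leans towards stopping sooner.** This is also fair. A reader might infer that patients are left less protected; a lower closure threshold does not do that. The problem is an undefined decision and an error rate that does not describe the combined rule.

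**The joint probabilities rest on chosen looks.** Correct, which is why they are illustrative. They show the direction and possible scale of the departure from 5%, not this trial's actual stopping probability.

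**Conclusion.** The point holds in conditional form and should be fixed. For the same event, denominator and look, the 60% closure criterion lies below every halt-for-review point (lowest 70.6%), and no text says which rule governs. The examples that matter are interim ones, such as 12-15 of 20 or 18-21 of 30; once 35 patients have been evaluated, accrual is complete and neither action changes enrolment.

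A reader might infer that the list is miscalculated. It is not: 4.99% at a true 50% matches the plan. What fails is using that figure as the chance of stopping for wound complications when X.B.ii also applies. The 29.4% figure assumes X.B.ii looks at 20 and 30, the list checked after every patient, the same event in both rules, and no stopping from the grade 4 or grade 5 rules. Other looks move it between 16.8% and 45.4%.

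The threshold comparison and the event mislabel follow from the text and need no assumed looks or event rates; the ordering needs only the like-for-like condition.

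**What to change.** 1. In IX.A.iv, replace the event label with grade 3-4 post-operative wound complications among patients with full follow-up, matching IX.A.iii.
2. Reconcile X.B.ii with the list in one of two ways:
   - make the IX.A.iv list the single wound-complication rule and have X.B.ii refer to it; or
   - keep the 60% threshold, but with the same grade and denominator as the list, a stated minimum number of patients, stated looks and a stated action.
3. Report the probability of stopping for the resulting rule at several true rates, for example 35%, 40%, 50% and 60%.

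The cost is a wording amendment and a short calculation. Sample size, visits and the printed X/N values need not change.

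The choice in item 2 is a safety trade-off that the sponsor should see first. Without the 60% rule, the chance of a halt at a true rate of 60% is 24.6%. Keeping it with looks at 20 and 30 raises that to 68.2%, but also raises the chance of stopping from 0.7% to 6.4% at a true 40%, the top of the range the protocol expects.

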- i. Treatment interruptions should be minimized. More than a 2-week interruption (holidays and weekend are not included) will be considered a major violation.
- ii. Long term adverse effects will be measured 4 months after radiation for years 1 and 2

Table 3: Compliance Criteria

Per Protocol	90% of the PTV is covered with that prescription dose. No more than 10% of the PTV receives a dose that is >110% of the prescribed dose.
Minor Deviation	Greater than 10%, but no more than 20% of PTV receives ≥ 110% prescription dose. Exceeding normal tissue tolerances by >2.5%
Major Deviation	The minimum dose to any volume falls below 90% of the prescribed dose. Or, more than 20% of PTV receives ≥ 110% prescription dose. Dose to the normal tissue structure(s) is > 5%

H. Adverse Events

- i. PLACEMENT OF FLAP: Flap reconstruction and/or placement at the time of resection or soon after resection within 1 month does not constitute as a graded toxicity, as these surgeries are done to close the primary wound. Flaps are often needed as STS are large and the tissue defect caused by surgery is not able to be primarily closed. In this setting, this does not constitute as a wound complication as the flap is used for closure. Should a flap need to be placed because of a wound complication after primary resection and final closure (either primarily or with a flap), then this would constitute as a CTC AE v 4.0 Grade 4 toxicity.
- ii. Acute: Wound complications are expected to develop in about 30-40% of patients. Other common radiation adverse events include if applicable to site of lesion: fatigue, regional alopecia, diarrhea, skin erythema and desquamation within the treatment fields, and reduction in blood counts.

- iii. Long-term: Common long-term treatment adverse events include: lymphedema of the extremity receiving radiation and surgery, subcutaneous fibrosis, and joint stiffness. Much less common radiation adverse events include osteoradionecrosis and bony fracture in the radiation field. There also is a risk of cancer occurring in a previously irradiated field.
- iv. All AE's grade 3, 4 or 5 will be collected. AE's that are grade 1 or 2 will not be collected. AE's will be captured for up to 2 years post treatment, death, or initiation of a new therapy, whichever occurs first. Planned flaps are not considered an adverse event.
- v. Table 5: Criteria for Early Closure or Dose Modification.

Grade 4 Toxicity (per CTCAEv4.0)	

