Number of Events Prior to termination of accrual and evaluation of dose	>2
Evaluation	Assessment of treating physician, daily follow-ups with members of the radiation oncology department with toxicity specific management, documentation of care and progress.
Time to re-initiate Radiation	Once a grade 4 toxicity has resolved and at the discretion of treating radiation oncologist, the patient will be taken off study and treated to a lower dose per fraction. The physician will then close the study.
Action	Closure of trial

- vi. The treating radiation oncologist will hold any radiation treatments as they feel is necessary due to the acute grade 3 or higher toxicity and the timing of re-initiation will be determined by the treating radiation oncologist, but will generally be when the grade 3 or higher toxicity resolves.
- vii. Post-operative wound complications (not acute during radiation, as defined on Appendix III (Radiation dermatitis) are listed.
- viii. If there are any grade 5 post-operative wound complications (Appendix III), then accrual will be halted and the protocol will be reviewed.

I. Documentation Requirements

- i. Treatment interruptions should be avoided when possible by preventative medical measures and nutritional and psychological counseling. Treatment breaks and reasons need to be clearly documented.

J. Compliance Criteria

- i. Section 6 describes appropriate conduct for treatment planning dosimetry. Criteria for both major and minor deviations are provided in Section 6.7.

K. Drug Therapy

- i. Chemotherapy will be delivered prior to radiation at the discretion of the medical oncologists. Prior to radiation, patients will have a repeat MRI scan. Chemotherapeutic regimens will be determined at the discretion of the medical oncologist.

- ii. There are no concomitant medications excluded for this patient population, with exception to chemotherapy. No chemotherapy will be delivered during this course of radiation therapy.

L. Surgery

- i. Patients will have surgical resection 4 to 8 weeks after completion of radiation therapy. Prior to surgery patients will have repeat MRI scan with DCE and DWI sequences. (this is standard practice at our institution and would be done for patients not on protocol).

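### A patient taken off study for grade 4 toxicity appears to leave follow-up too, so later wound, late-toxicity and local-control outcomes may be lost because of toxicity

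*Combined protocol and SAP*

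**What the plan says.** Section X of the protocol carries a single heading on subject withdrawal. Within it:

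- X.B.i: "If a patient has a grade 4 or higher toxicity, then they will be taken off the study, administered a lower dose per fraction".
- X.D: "Subjects will not be replaced".
- X.E: "Follow up and data collection for withdrawn subjects will terminate at the time of withdrawal".

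Table 5 (VI.H.v) repeats the removal, timed after the grade 4 event has resolved: "the patient will be taken off study and treated to a lower dose per fraction".

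Two closure thresholds stand side by side. The first sentence of X.B.i gives "Greater than 2 patients who have any grade 4 or higher toxicity during radiation", and Table 5 also uses more than 2 events. X.F.i gives "If any grade 4 toxicity occurs, the dose will be modified based on the BED calculator above and the study will be closed", and the second sentence of X.B.i likewise closes the study after a single patient.

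The general follow-up provisions are these. VI.H.iv says "AE's will be captured for up to 2 years post treatment, death, or initiation of a new therapy, whichever occurs first". XI.C.i sets at least 2 years of follow-up for disease-free survival. VII and Table 4 schedule visits every 4 months for 2 years after surgery. None of them mentions patients removed for toxicity. Nowhere does the protocol distinguish stopping protocol radiation from leaving the study, and it defines no analysis population.

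**The concern.** A grade 4 event during radiation comes before everything the trial sets out to measure. Surgery follows radiation by 4 to 8 weeks (VI.L.i). The wound check, late-toxicity visits and MRI for local recurrence all follow surgery. If the patient's data stop at removal, all of these outcomes are missing, and the reason they are missing is toxicity of the regimen under study.

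Such loss is informative. A patient with severe acute toxicity may well have a different risk of wound breakdown or late effects. A patient whose radiation was changed may have a different risk of local recurrence. Dropping such patients, or censoring them at removal, treats them as if they resembled those who stayed. In a 35-patient trial with a pass mark of at most one recurrence, a single unobserved outcome can decide the result.

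**Working it through.** **1. The plan's own figure.** XIII.B and XIII.C give a type I error of 0.0897 at a true 12% recurrence rate and power of 81.0% at 2.5%, for at most 1 recurrence in 35. The formula is

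P(X ≤ 1) = (1 − p)^n + n·p·(1 − p)^(n−1).

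For n = 35 and p = 0.12: 0.88^35 + 35 × 0.12 × 0.88^34 = 0.0114 + 0.0544 = 0.0658.

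| Patients followed | Type I error (p = 0.12) | Power (p = 0.025) |
|---|---|---|
| 35 | 0.0658 | 0.782 |
| 34 | 0.0730 | 0.791 |
| 33 | 0.0810 | 0.801 |
| 32 | 0.0897 | 0.810 |

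The stated figures are not reproduced at 35; they are the values for 32, where 1/32 = 3.1%. That is a separate matter. Here the table shows that non-informative loss of one to three patients keeps the type I error below the nominal 10%.

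**2. How many patients.** If any grade 4 event closes the study, one patient is removed. If more than 2 are needed, the third triggers closure, so about three are removed (more if several are under treatment at once). Under the single-event reading accrual may stop short of 35, so the counts below assume either the higher threshold or a removal near the end of accrual.

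**3. Local control.** Assume one patient is removed and the other 34 have one recurrence.

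- Removed patient unobserved: 1/34 = 2.9%, a pass if the at-most-one rule is applied to those followed.
- Removed patient in fact recurs and is counted: 2/35 = 5.7%, a fail.

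Scoring the missing patient as a recurrence at analysis is a poor substitute for following the patient. A pass would then need no recurrence among the other 34, and power at a true 2.5% would be 0.975^34 = 0.423.

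**4. Wound boundary.** IX.A.iii counts only patients whose follow-up is complete. Take the listed pairs in IX.A.iv, and between listed sample sizes use the count of the next listed pair. Assume each removed patient would have had a grade 3–4 wound complication.

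| All patients observed | Removed, unobserved | Count seen | Count needed | Result |
|---|---|---|---|---|
| 14/18, halt | 1 | 13/17 | 14 | no halt |
| 20/27, halt | 2 | 18/25 | 19 | no halt |
| 25/35, halt | 1 | 24/34 | 24 | halt |
| 25/35, halt | 2 | 23/33 | 24 | no halt |

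So one or two unseen events can delay a halt, though one does not always do so. Two qualifications apply. IX.A.iii describes the boundary as one on wound complications, while IX.A.iv lists the pairs for treatment-related grade 3–4 events; the table follows IX.A.iii. And 13/17 = 76.5% is already above the 60% wound-complication criterion in X.B.ii. That criterion has the same weakness: 12/20 = 60.0% meets it, and 11/19 = 57.9% does not.

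**The case against.** The case against has real force on several points.

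- **The acute event is not lost.** A reader might infer that the grade 4 toxicity itself disappears. The documents do not support this. Table 5 removes the patient only after resolution and asks for daily follow-up and documentation until then. VI.H.iv collects grade 3 to 5 events, and IX.A.ii adds: "Grades 4 & 5 events must be reported to the DSMC within 5 calendar days of study staff's knowledge". This stands; only later outcomes are at risk.
- **Off study is never equated with withdrawn.** X.A and X.B.iii use withdrawal for a patient's own choice, so X.E could be meant only for that. This stands in part. The shared heading and the lack of any other rule for removed patients make the wider reading the natural one, but it remains an inference. At the least, site staff cannot tell whether to go on collecting data.
- **VI.H.iv does not plainly contradict X.E.** It sets a maximum and also ends at a new therapy, which might or might not include modified radiation. This stands; the two need reconciling but are not in clear conflict.
- **The results need not describe only patients who tolerated the full schedule.** Under VI.H.vi, patients with grade 3 toxicity may have radiation held and resumed, without removal. No denominator is stated, and removed patients could be censored under the time-to-event methods in XIV.A. This stands, so bias is possible, not certain.
- **Few patients are involved, and the type I error stays below 10%.** This also stands. What it does not answer is that the few are selected by toxicity.

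**Conclusion.** The point holds as a gap in follow-up wording with a small but informative effect. As the text most naturally reads, one to about three patients would contribute their acute grade 4 event and nothing afterwards. The wound, late-toxicity and local-control results may then lean in the favourable direction.

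This rests on reading removal for toxicity as withdrawal under X.E, and on removed patients being dropped or censored, since the plan does not say how they count. The decision examples use assumed outcomes for removed patients; they show what could happen and do not predict it.

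A reader might infer that the type I error is pushed past its limit. The calculation shows otherwise: 0.066 to 0.090 for 35 down to 32 patients. A reader might also infer from X.F.i, which is not tied to the radiation period, that patients with post-operative grade 4 wound complications are removed as well. X.F.i speaks of dose and of closing the study, not of removing the patient, and the first sentence of X.B.i concerns toxicity during radiation, so the documents do not establish this. The change is a cheap improvement, but it has to be made before the data are lost, because uncollected outcomes cannot be recovered at analysis.

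**What to change.** - In X.B.i and Table 5, state that a patient removed for toxicity leaves protocol radiation but remains in study follow-up on the Table 4 schedule.
- Limit X.E to patients who withdraw consent for follow-up.
- State that every patient who starts protocol radiation stays in the toxicity, wound, local-recurrence, disease-free survival and overall survival analyses, with the dose actually delivered recorded.
- Reconcile X.F.i, both sentences of X.B.i and Table 5, which give different closure thresholds. No view is taken here on which threshold or dose is right.

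The cost is a protocol amendment and a little more data collection for a few patients. The pre-surgery MRI, the wound check and the first follow-up imaging are described in VI.L.i, VII.B and VII.C as standard practice. FACT-L and MSTS are not so described and would be added work. Reported rates may look slightly less favourable.

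### X.F.i closes the study at any grade 4 toxicity, X.B.i and Table 5 set the threshold at more than 2, and nothing says which rule governs the first or second event

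*Combined protocol and SAP*

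**What the plan says.** Three places in the combined protocol and SAP deal with closing the study for grade 4 toxicity.

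- **Section X.F.i (Dose Modification):** "If any grade 4 toxicity occurs, the dose will be modified based on the BED calculator above and the study will be closed". It gives no count, no time window and no cross-reference to the other two places.
- **Section X.B.i (Criteria for early Closure):** the criterion is "Greater than 2 patients who have any grade 4 or higher toxicity during radiation". The following sentence turns to a single affected patient, who is taken off study, "administered a lower dose per fraction per the treating physician, and the study will be closed".
- **Table 5 (section VI.H.v):** the row "Number of Events Prior to termination of accrual and evaluation of dose" carries the entry >2, and the action is closure of the trial. The row on re-initiating radiation speaks of one resolved grade 4 toxicity, takes that patient off study at a lower dose per fraction, and ends "The physician will then close the study".

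Section VI.H.vi lets the radiation oncologist hold treatment for acute toxicity of grade 3 or above and says that resumption "will generally be when the grade 3 or higher toxicity resolves". It does not mention closing the study.

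Post-operative wound complications have separate rules in X.B.ii, VI.H.viii and IX.A.iii-iv.

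**The concern.** A stopping rule has to tell the site what to do when the event happens. Here, with one or two affected patients, X.F.i closes the trial, while the explicit count in X.B.i and Table 5 leaves it open until the third. The conflict is not only between sections: X.B.i and Table 5 each pair a count of more than 2 with a sentence that closes the study after one patient.

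The investigator and the DSMC could therefore take opposite actions on the same event, and each could cite the protocol. Continuing would breach X.F.i. Closing would end the trial below a threshold stated twice, possibly with fewer than the 35 patients for which section XIII specifies the primary test.

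**Working it through.** **Step 1. The texts side by side.**

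| Place | Trigger for closing the study | Unit | Grade | Window stated |
|---|---|---|---|---|
| X.F.i | any occurrence | not stated | 4 | none |
| X.B.i, first sentence | more than 2 | patients | 4 or above | during radiation |
| X.B.i, sentence on a single patient | one | patient | 4 or above | none of its own |
| Table 5, threshold row | more than 2 | events | 4 | none |
| Table 5, re-initiation row | one | patient | 4 | none |

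Single-event closure wording appears three times and the count of more than 2 appears twice. No sentence ranks them or ties X.F.i to the third event. VI.H.vi concerns holding and resuming radiation, so it does not settle the matter.

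**Step 2. What follows at each count of affected patients.**

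| Affected patients | Any grade 4 event closes | More than 2 closes |
|---|---|---|
| 0 | open | open |
| 1 | closed | open |
| 2 | closed | open |
| 3 | closed | closed |

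The rules part at the first event.

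**Step 3. Illustration of size.** The plan states no error rate or closure probability for this rule, so there is no figure to reproduce.

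Inputs: n = 35 (section X.A). The per-patient probability p of a qualifying grade 4 toxicity is an assumption, because the documents give no rate; XI.C.iii says only that minimal toxicity is expected. I take p = 1%, 2% and 5%, independent patients, and the same p under both rules.

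Closure at any event: 1 − (1 − p)^35.

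- p = 1%: 1 − 0.99^35 = 1 − 0.7034 = 0.2966
- p = 2%: 1 − 0.98^35 = 1 − 0.4931 = 0.5069
- p = 5%: 1 − 0.95^35 = 1 − 0.1661 = 0.8339

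Closure at more than 2 patients: 1 − P(0) − P(1) − P(2), with P(1) = 35·p·(1 − p)^34 and P(2) = 595·p²·(1 − p)^33.

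- p = 1%: 1 − 0.7034 − 0.2487 − 0.0427 = 0.0052
- p = 2%: 1 − 0.4931 − 0.3522 − 0.1222 = 0.0325
- p = 5%: 1 − 0.1661 − 0.3059 − 0.2737 = 0.2542 (from unrounded terms)

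| Assumed p | Closed under any | Closed under more than 2 |
|---|---|---|
| 1% | 30% | 0.5% |
| 2% | 51% | 3% |
| 5% | 83% | 25% |

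The gap between the columns is the chance of finishing with exactly 1 or 2 affected patients. It does not measure how often the rules disagree during the trial. Disagreement starts at the first event, so on these assumptions its probability is the middle column.

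**The case against.** The strongest reply is that this is loose drafting rather than two rival rules. X.F.i sits under dose modification, not under closure criteria. X.B.i itself uses the word any for the kind of toxicity while requiring a count above 2, so the word in X.F.i need not mean the first event. The closure sentences in all three places could then describe the action once the count is reached. That reading is possible, but the words of X.F.i do not state it: the section has its own trigger and refers to no count. A site cannot be expected to supply the link.

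Some of the apparent differences in scope do shrink on inspection. An affected patient comes off study, so patients and events nearly coincide. Table 5 speaks of re-initiating radiation and X.F.i of modifying the dose, which makes sense mainly while radiation is under way.

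The safeguards also stand. Under IX.A.ii, grade 4 and 5 events reach the DSMC within 5 calendar days, and under IX.A.vi the committee can terminate the study. This limits the risk to patients and lowers the severity. It does not say which rule the protocol imposes.

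**Conclusion.** The point holds as an internal inconsistency in a safety stopping rule, of moderate severity. The contradiction rests on the text alone and on no assumed rate. Its practical size does depend on the rate: at assumed rates of 1% to 5%, closure has probability 30% to 83% under one rule and 0.5% to 25% under the other, given independent patients, full accrual of 35 unless closed, and a common p.

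Four stronger conclusions that a reader might draw are not supported.

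- *Patients are left exposed.* X.B.i and Table 5 take the affected patient off protocol dosing, and the stricter rule errs towards closure.
- *One post-operative grade 4 wound event closes the trial.* VI.H.i does grade some later flaps as 4, and X.F.i states no window. But its remedy is a change of radiation dose, and post-operative wound events have their own rules.
- *A patient taken off study for toxicity is lost to follow-up.* X.E ends data collection for withdrawn subjects, and VI.H.iv ends adverse event capture at a new therapy. X.A and X.B.iii use withdrawal for the patient's own choice, and nothing says that either provision covers these patients.
- *The rule must extend to surgery.* Resection follows 4 to 8 weeks after radiation (VI.L.i), but toxicity is evaluated before surgery (Table 4) and grade 4 events are reported to the DSMC. A longer window is the sponsor's choice and is not needed to remove the conflict.

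The definition of the primary endpoint and its test in section XIII do not depend on which rule is right.

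**What to change.** State one rule identically in X.B.i, X.F.i and Table 5. The default is the threshold already given twice, with the unit, grade range and window of X.B.i: *close the study when more than 2 patients have had toxicity of grade 4 or above during radiation*.

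Then rewrite X.F.i, the single-patient sentence in X.B.i and the re-initiation row of Table 5 as patient-level actions only: stop protocol dosing and give a lower dose per fraction, with no study closure at a single event.

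If the sponsor intends closure at the first event, replace the count of more than 2 in X.B.i and Table 5 instead and leave the single-event sentences as they are.

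Leave post-operative wound events to X.B.ii, VI.H.viii and IX.A.iii-iv. X.E and VI.H.iv need no edit for this point.

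The cost is a wording amendment in three places, with no change to sample size, visits or the primary analysis.
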